#### **4.1.6 Discontinuation of Investigational Product**

An individual subject in any of the treatment arms will not receive any further study drug if any of the following occur in the subject in question:

- 1 Withdrawal of consent
- 2 Any toxicity/AE that in the opinion of the investigator and/or the sponsor, warrants discontinuation of further dosing
- 3 Any AE that meets criteria for discontinuation as defined in the Toxicity Management Guidelines (see Section [3.1.3](#))
- 4 Pregnancy or intent to become pregnant (Section [5.6.2](#))
- 5 Delay of more than 56 days from the last administration of study drug to the next planned dose
- 6 Confirmation of disease progression (Section [4.3.1](#))
- 7 Unconfirmed disease progression and investigator determination that the subject is not eligible for a confirmation scan (Section [4.3.1](#))
- 8 Initiation of alternative anticancer therapy
- 9 Intercurrent illness or medical condition, in the judgment of the investigator and/or the sponsor warrants discontinuation of further dosing

Subjects who are permanently discontinued from receiving study treatment will be followed for protocol-specified assessments, including follow-up of any AEs, unless consent is withdrawn from further study participation (Section [4.1.5](#)), disease progression, the subject starts alternative treatment/clinical study, or the subject is lost to follow-up. All subjects will be followed for survival until the end of the study unless consent is withdrawn from further study participation.

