#### 4.2.2 Follow-up Period

**Table 6** presents follow-up procedures for subjects who completed study treatment and maintain DC, subjects who discontinued study treatment due to other reason not related to PD (Section 4.1.6), and subjects who experienced unconfirmed PD and are eligible for a confirmation scan. Procedures for subjects who discontinue study treatment due to PD are provided in Section 4.2.3. Overall, all subjects continuing in the study must adhere to the study procedures for up to 5 years (from randomization) provided they achieve DC and remain disease free.

As OS is a late endpoint in this patient population, after the planned 5-year post randomization study period, subjects may be contacted for survival every 12 months.

**Table 6 Schedule of Follow-up Procedures: Subjects Who Completed Study Treatment and Maintain DC, Subjects Who Discontinued Study Treatment Due to Other Reason Not Related to PD, and Subjects Who Experienced Unconfirmed PD and are Eligible for a Confirmation Scan**

| Time since Cycle 1 Day 1                    | ≤ 12 Months                          | > 12 to ≤ 24 Months               | > 24 to 60 Months             |
|---|--------------------------------------|-----------------------------------|-------------------------------|
| Follow-up based on previous scheduled visit | Every 8 Weeks
(± 3 days)          | Every 12 Weeks
(± 7 days)      | Every 6 Months
(± 4 weeks) |
| Procedure                            |                                      |                                   |                               |
| Physical examination                        | X                                    | X                                 | X                             |
| Vital signs                                 | X                                    | X                                 | X                             |
| ECOG performance status                     | X                                    | X                                 | X                             |
| Serum chemistry                             | X                                    | X                                 | X                             |
| Thyroid function tests a         | X                                    | X                                 | X                             |

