#### 4.2.3 End of Study

**Table 7** presents procedures for the end of study visit for all subjects. End of study visit will be performed when a subject discontinues study due to a confirmed PD, or a subject experienced an unconfirmed PD but is not eligible for a confirmation scan, or after 60 months of follow-up for subjects who achieve DC and remain disease free, or at the last study visit for subjects who discontinue study due to reason not related to PD.

Subjects who discontinue treatment due to any reason, including confirmed PD or initiation of alternative anticancer therapy, will be followed for survival according to the timepoints in **Table 6** (every 8 weeks up to 12 months post Cycle 1 Day 1, every 12 weeks from > 12 to ≤ 24 months, and every 6 months from > 24 to 60 months post Cycle 1 Day 1) unless the subject withdraws consent from further participation in the study. After 60 months, subjects may be contacted for survival every 12 months until the end of the entire study.

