- PFS, defined as the time from randomization until the first documentation of disease progression according to RECIST v1.1 or death due to any cause, whichever occurs first, regardless of whether the subject receives subsequent anticancer therapy prior to progression. Subjects who are alive progression free at the time of DCO will be censored on the date of their last evaluable tumor assessment. PFS-12 will be estimated using the Kaplan-Meier method.

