### **3.4.2.2 Duration of Response**

Duration of response (DoR) is defined as the time from the first documentation of a subsequently confirmed OR until the first documentation of a disease progression or death due to any cause, whichever occurs first, regardless of whether the subject receives subsequent anticancer treatment prior to progression. Only subjects who have achieved OR (confirmed CR or confirmed PR) will be evaluated for DoR. DoR is defined in months as follows:

$$\text{DoR (months)} = (\text{Date of PD/death or censoring} - \text{Date of first confirmed disease response} + 1) / (365.25/12)$$

The date of PD/death or censoring is the same as defined for PFS in Section 3.4.2.4. The median DoR and its 95% CI will be estimated using the Kaplan-Meier method.

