### **3.4.2.4 Progression-free Survival**

Progression-free survival (PFS) is defined as the time from randomization until the first documentation of a disease progression or death due to any cause, whichever occurs first, regardless of whether the subject receives subsequent anticancer treatment prior to progression. Subjects who have no documented progression and are still alive at the time of analysis will be censored at the time of the latest date of assessment from their last evaluable RECIST v1.1 assessment. PFS is defined in months as follows:

$$\text{PFS (months)} = (\text{Date of PD/death or censoring} - \text{Date of randomization} + 1) / (365.25/12),$$

The censoring guidance and the date of PD/death or censoring are given in the table below. The number and percentage of subjects experiencing a PFS event and Kaplan-Meier plots of PFS will be presented by treatment group. The median PFS and its 95% CI will be estimated using the Kaplan-Meier method. The proportion of subjects progression-free and alive at 12

months (PFS-12) and associated 95% CI will be estimated using the Kaplan-Meier method. Additional PFS landmarks to be included in the final analysis are PFS-18, PFS-24, and PFS-36.

The difference in PFS between each experimental arm and control arm will be tested for significance by using a stratified log-rank test on histology (adenocarcinoma vs non-adenocarcinoma). The log-rank test will be carried out with the Breslow method for handling ties. The hazard ratio (HR) (experimental vs. control) with two-sided 95% CI will be estimated by stratified Cox regression model on histology with ties handled by the Efron method ([Efron et al, 1977](#)).

The comparison of PFS-X (X=12, 18, 24, 36 months) between each experimental arm and control arm will be performed by normal approximation under complementary loglog (cloglog) transformation ([Klein et al, 2007](#)). The test statistic shown below asymptotically follows a chi-square distribution with one degree of freedom under the null hypothesis  $H_0: S_1(t) = S_2(t)$ .

$$X^2 = \frac{\left( \log(-\log(\hat{S}_1(t))) - \log(-\log(\hat{S}_2(t))) \right)^2}{\hat{\sigma}_1(t)^2 / \left( \log(\hat{S}_1(t)) \right)^2 + \hat{\sigma}_2(t)^2 / \left( \log(\hat{S}_2(t)) \right)^2}$$

where

- $\hat{S}_k(t)$ , with  $k = 1, 2$  is the Kaplan-Meier estimate of the survival function for the  $k$ th treatment group

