**Table 3.4.1      Summary of Censoring Guidelines for PFS**

Situation	Date of PD/Death or Censoring	PFS Outcome
Documented Progressive Disease (PD) or death	Date of earliest sign of PD or death, whichever comes first	Event (unless the censoring rule specified below)
Death or PD immediately after $\geq 2$ consecutive missed or non-evaluable disease assessments as per the protocol specified assessment schedule	Date of last progression-free disease assessment prior to missed or non-evaluable assessments, or randomization, whichever occurred last	Censored
No PD or death at time of analysis or lost to follow-up	Date of last evaluable progression-free disease assessment	Censored
No tumor assessment at baseline and no evidence of PD at first post-baseline disease assessment OR No tumor assessment post-first dose, and no death prior to second scheduled post-baseline disease assessment	Date of randomization	Censored

PD = progressive disease; PFS = progression-free survival.

Subjects having missing lesion data at baseline or no disease assessments post-first dose of IP will have PFS censored at the date of randomization unless the subject dies prior to the second scheduled post-baseline disease assessment in which case the death date will qualify as a PFS event.

If a subject has two or more consecutive completely missed or non-evaluable assessments followed immediately by death or an assessment showing radiologic disease progression, then the subject will be censored for PFS. PFS will be censored at the date of randomization or the last progression-free disease assessment prior to the missed or non-evaluable assessments, whichever occurred last.

If a subject has two or more consecutively missed or non-evaluable assessments followed by an assessment showing no radiologic disease progression, then the assumption will be that the subject did not progress during the missed or non-evaluable assessments.

The length of gap (in number of days) to determine two or more consecutive assessments is defined as the following:

- 126 days during the first 12 months (A 8-week disease assessment interval plus a 7-day window for each assessment).

- 182 days from month 12 to month 24 (A 12-week disease assessment interval plus a 7-day window for each assessment).
- 422 days after month 24 (A 6-month disease assessment interval plus a 4-week window for each assessment).

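### Protocol 4.1.6 and Table 6 conflict on scans after alternative therapy; where 4.1.6 is followed, PFS and SAP DoR are in effect censored at new therapy, contrary to their definitions

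*Protocol*

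**What the plan says.** **Endpoint definitions.** Protocol 4.8.3 counts PFS events "regardless of whether the subject receives subsequent anticancer therapy prior to progression". SAP 3.4.2.4 says the same: "regardless of whether the subject receives subsequent anticancer treatment prior to progression". SAP 3.4.2.2 attaches this clause to DoR and adds: "The date of PD/death or censoring is the same as defined for PFS in Section 3.4.2.4". The DoR definition in protocol 4.8.3 does not contain the clause.

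**Follow-up rules.** Protocol 4.1.6 deals with subjects permanently taken off study drug. It keeps them on protocol-specified assessments until one of several events, including "disease progression, the subject starts alternative treatment/clinical study, or the subject is lost to follow-up", and then secures survival follow-up only. Protocol 4.2.2 assigns the Table 6 schedule, which includes scans, to several groups, among them "subjects who discontinued study treatment due to other reason not related to PD (Section 4.1.6". Item 8 of the 4.1.6 list is the start of alternative anticancer therapy. Protocol 4.2.3 states that subjects who stop treatment for any reason, "including confirmed PD or initiation of alternative anticancer therapy, will be followed for survival", and says nothing about their scans.

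**Censoring rules.** SAP Table 3.4.1 has no row for subsequent therapy. A subject without progression or death is censored at the last evaluable progression-free scan. The text under the table adds a gap rule: "If a subject has two or more consecutive completely missed or non-evaluable assessments followed immediately by death", or by a scan showing progression, PFS is censored at the last progression-free assessment before the gap (or at randomization, if later). The gap is set at 126 days in the first 12 months, 182 days from month 12 to 24, and 422 days after that.

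**The concern.** A PFS definition that ignores subsequent therapy needs scans after that therapy starts. If 4.1.6 governs, those scans are not required, and the SAP rules turn the missing data into censoring at or before the switch. The report would then describe the estimate as regardless of subsequent therapy when, for these subjects, it censors at subsequent therapy.

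The endpoints at stake are secondary but are compared formally. SAP 3.4.2.4 plans a stratified log-rank test, a Cox hazard ratio and tests of PFS at 12, 18, 24 and 36 months, and SAP 3.4.4 adds subgroup forest plots of PFS hazard ratios. The study is open-label, so the decision to switch could differ by arm. No sensitivity analysis is planned for this case.

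**Working it through.** **1. The two follow-up rules side by side.** Take a subject who starts another anticancer therapy without documented progression. Under 4.1.6 the protocol-specified assessments end. Under 4.2.2 and Table 6 the subject stopped for a reason in 4.1.6 other than PD, so scans continue. Both texts are current and one cites the other. The protocol does not say which governs.

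**2. SAP gap limits.** Each is 2 × (interval + window), taking 6 months as 183 days:
- first 12 months: 2 × (56 + 7) = 126 days
- months 12 to 24: 2 × (84 + 7) = 182 days
- after month 24: 2 × (183 + 28) = 422 days

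All three reproduce.

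**3. What the rules do to one subject (invented dates).** The last clean scan is on day 112, new therapy starts on day 130, and scans stop under 4.1.6. The gap limit falls on day 112 + 126 = 238.
- Alive at analysis: censored at day 112, whatever happened to the tumor.
- Dies on day 230 (gap 118 days): PFS event.
- Dies on day 250 (gap 138 days): censored at day 112, although survival follow-up recorded the death.

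**4. Effect on PFS-12.** The documents give no switching rate and no PFS assumption for this trial. Assumptions: exponential PFS with the median of 17.2 months that protocol 1.1 cites for durvalumab, and a share f of would-be progressors censored at the last scan before progression, with none of their deaths counted. In continuous time the counted hazard is multiplied by (1 − f), so Kaplan-Meier PFS-12 tends to 0.5^(12(1 − f)/17.2). A simulation with scans every 8 weeks to month 12, every 12 weeks to month 24 and then every 6 months gives slightly higher levels, because progression is dated at scans.

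| f (assumed) | Formula | Simulated | Simulated rise (points) |
|---|---|---|---|
| 0% | 61.7% | 64.1% | 0 |
| 5% | 63.2% | 65.6% | 1.5 |
| 10% | 64.7% | 66.9% | 2.9 |
| 20% | 67.9% | 69.9% | 5.8 |

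(Rises are taken from the unrounded values.) For scale, 100 − 61.7 = 38.3% of an arm of 60, about 23 subjects, would have an event by month 12. Of these, 5% to 10% is 1 to 2 subjects.

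**5. Effect on the hazard ratio.** By the same argument, observed HR ≈ true HR × (1 − f_exp)/(1 − f_control). The simulated values are from an unstratified Cox model with Efron ties and 20,000 subjects per arm, at true HR 0.70.

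| f control | f experimental | Formula | Simulated |
|---|---|---|---|
| 0% | 0% | 0.70 | 0.705 |
| 10% | 10% | 0.70 | 0.705 |
| 20% | 20% | 0.70 | 0.689 |
| 0% | 10% | 0.63 | 0.63 |
| 10% | 0% | 0.78 | 0.77 |
| 5% | 20% | 0.59 | 0.60 |
| 20% | 5% | 0.83 | 0.82 |

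Equal switching leaves the ratio almost unchanged. Unequal switching moves it in either direction.

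**The case against.** The strongest reply is that Table 6 already keeps these scans, so the endpoint can be derived wherever sites follow it. That stands against the stronger reading a reader might take from 4.1.6 alone, namely that scans stop for every switcher and that PFS as defined cannot be derived. The documents show a conflict, not a uniform stop.

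Other stronger readings also lack support:
- **4.2.3 as a scan-stopping rule.** Its sentence covers every reason for stopping treatment and concerns survival contact. Read as ending scans, it would cancel Table 6 for everyone who discontinues.
- **All later deaths are lost.** Deaths within the gap limits count. Table 3.4.1 also ties missed assessments to the protocol schedule, so it can be argued that a scan the protocol ended was not missed. The day counts make no such exception, so this stays unsettled.
- **Censoring just before likely progression.** The documents do not say why or how often subjects switch before RECIST progression. Protocol 4.3.1 allows extra scans when clinically indicated, and SAP 7.1.5 dates PD at the first objective test showing it. A worsening subject scanned before switching is therefore an event.
- **A bias of 4 to 8 points in PFS-12.** Suppose PFS is 70% at month 6 and 50% at month 12, and 5 or 10 of 100 subjects switch just after month 6, all of whom would progress by month 12. Kaplan-Meier then reads 0.70 × 50/65 = 53.8% or 0.70 × 50/60 = 58.3%. But only 20 of 100 progress in that window, so this requires 25% or 50% of them to switch before documented PD, in one arm only. It is close to a worst case.

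Scope is limited as well. ORR, the primary endpoint, counts only responses before subsequent therapy (SAP 3.4.1.1), and the sample size rests on precision of the ORR difference, not on power for PFS.

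What survives is the conflict itself and the missing SAP rule for subjects whose scans did stop.

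**Conclusion.** The point holds as a conflict between sections with a conditional effect on secondary endpoints. Protocol 4.1.6 and 4.2.2/Table 6 give opposite instructions for subjects who start alternative therapy without RECIST progression. Where 4.1.6 is followed, PFS in both documents and DoR in the SAP are no longer the endpoints as defined: the subject is censored at the last evaluable scan, and so is a death beyond 126, 182 or 422 days.

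The text conflict is certain; the size is not. With an assumed 5% to 10% of would-be progressors affected, PFS-12 is too high by about 1.5 to 3 points. The hazard ratio is materially biased only if switching differs by arm: at 10% against 0%, a true 0.70 reads 0.63 or 0.77 depending on the arm. The documents give no evidence that switching differs, but an open-label design does not exclude it.

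**What to change.** **Protocol.** Reconcile 4.1.6 with 4.2.2 and Table 6. Remove the start of alternative treatment as a reason to end disease assessments, so that subjects without RECIST progression stay on the scans Table 6 already schedules, and align 4.2.3. Amendment 4 records that all subjects have completed treatment, so this helps only those still in scan follow-up and cannot recover scans already omitted.

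**SAP.**
- Report per arm how many subjects started subsequent therapy before documented PD, and whether their scans continued.
- Keep the main rules of Table 3.4.1 and add PFS and DoR sensitivity analyses that (a) count later deaths as events despite missed scans and (b) count the start of subsequent therapy as an event. A special death rule for switchers in the main analysis is debatable, because it would treat equal gaps differently according to their cause.
- Align the protocol and SAP definitions of DoR.

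**Cost.** A few additional scans, the approvals that protocol 7.4 requires for an amendment, and a small amount of analysis. The SAP part should need no new data: SAP 3.4.2.5 lists the start dates of alternative anticancer treatment among the dates on the case report forms, and SAP 3.3.3 already plans a summary of subsequent treatment if data allow.

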#### **4.1.7 Replacement of Subjects**

Subjects will not be replaced.

#### **4.1.8 Withdrawal of Informed Consent for Data and Biological Samples**

MedImmune ensures that biological samples are returned to the source or destroyed at the end of a specified period as described in the informed consent.

If a subject withdraws consent to the use of donated biological samples, the samples will be disposed of/destroyed, and the action documented. If samples are already analyzed, MedImmune is not obliged to destroy the results of this research. As collection of the biological samples (except for the optional tumor biopsy at screening and on-treatment, and optional blood sample at screening for germline DNA) is an integral part of the study, if a

subject decides to withdraw consent to the use of donated biological samples, then the subject will also be withdrawn from further study participation.

The Principal Investigator:

- Ensures subject's withdrawal of informed consent to the use of donated samples is notified immediately to MedImmune.
- Ensures that biological samples from that subject, if stored at the study site, are immediately identified, disposed of/destroyed, and the action documented.
- Ensures the organization(s) holding the samples is/are informed about the withdrawn consent immediately and that samples are disposed of/destroyed, the action documented and the signed document returned to the study site.
- Ensures that the subject and MedImmune are informed about the sample disposal.

MedImmune ensures the organizations holding the samples is/are informed about the withdrawn consent immediately and that samples are disposed of/destroyed and the action documented and returned to the study site.

## 4.2 Schedule of Study Procedures

The schedule of study procedures outlined in this section, with the exception of study drug administration that is treatment-arm specific, will be followed for all treatment arms.

The study drug treatment regimens for the control arm and each combination experimental arm are presented in Section [3.1.2](#).

### 4.2.1 Enrollment/Screening and Treatment Periods

[Table 5](#) shows all procedures to be conducted during the screening and treatment periods.

**Table 5** Schedule of Screening and Treatment Period Procedures

| Procedure                           | Screening            | Treatment Period: Up to 12 Months
28-day Cycles |                          |                          |                          |  |
|-------------------------------------|----------------------|--|--------------------------|--------------------------|--------------------------|--|
|                                     |                      | Cycle 1  | Cycle 2                  | Cycle 3                  | Cycle 4                  | Cycle 5 through Cycle 13                       |
|                                     | Day -28 to
Day -1 | Day 1
( $\pm$ 3 days)                           | Day 1
( $\pm$ 3 days) | Day 1
( $\pm$ 3 days) | Day 1
( $\pm$ 3 days) | Day 1
( $\pm$ 3 days)                       |
| Written informed consent            | X                    |  |                          |                          |                          |  |
| Demographics                        | X                    |  |                          |                          |                          |  |
| Medical history a        | X                    |  |                          |                          |                          |  |
| Verify eligibility criteria         | X                    |  |                          |                          |                          |  |
| Physical examination                | X                    | X  | X                        | X                        | X                        | X  |
| Vital signs                         | X                    | X  | X                        | X                        | X                        | X  |
| ECG b                    | X                    |  |                          |                          |                          |  |
| ECOG performance status             | X                    | X  | X                        | X                        | X                        | X  |
| Tumor specimen c         | X                    |  |                          |                          |                          | X (optional) c                      |
| Serum chemistry                     | X                    | X d                                     | X                        | X                        | X                        | X  |
| Hematology                          | X                    | X d                                     | X                        | X                        | X                        | X  |
| Urinalysis                          | X                    | As clinically indicated                            |                          |                          |                          |  |
| Thyroid function tests e | X                    | X d                                     | X                        | X                        | X                        | X  |
| Pregnancy test f         | X                    | X  | X                        | X                        | X                        | X  |
| Coagulation parameters              | X                    |  |                          |                          |                          |  |
| Hepatitis B and C; HIV g | X                    |  |                          |                          |                          |  |
| Concomitant medications             | X                    | X  | X                        | X                        | X                        | X  |
| Assessment of AEs/SAEs              | X                    | X  | X                        | X                        | X                        | X  |
| Disease assessment (scans)          | X h       |  |                          | X
(within 7 days)     |                          | Cycle 5 then every 2 cycles
(within 7 days) |

**Table 5** Schedule of Screening and Treatment Period Procedures

| Procedure                              | Screening         | Treatment Period: Up to 12 Months
28-day Cycles |                          |                          |                          |   |
|--|-------------------|--|--------------------------|--------------------------|--------------------------|---|
|  |                   | Cycle 1  | Cycle 2                  | Cycle 3                  | Cycle 4                  | Cycle 5 through Cycle 13                            |
|  | Day -28 to Day -1 | Day 1
( $\pm$ 3 days)                           | Day 1
( $\pm$ 3 days) | Day 1
( $\pm$ 3 days) | Day 1
( $\pm$ 3 days) | Day 1
( $\pm$ 3 days)                            |
| Brain MRI (preferred) or CT            | X h    |  |                          |                          |                          |   |
| PET scan                               |                   |  |                          |                          |                          | Cycle 7 only
(within 7 days of Day 1)            |
| CCI [REDACTED]                         | [REDACTED]        | [REDACTED]   | [REDACTED]               | [REDACTED]               | [REDACTED]               | [REDACTED]  |
| [REDACTED]                             | [REDACTED]        | [REDACTED]   | [REDACTED]               | [REDACTED]               |                          |   |
| [REDACTED]                             | [REDACTED]        |  | [REDACTED]               |                          |                          |   |
| Serum for PK                           |                   | X (predose & EOI) i                     | X (predose) j |                          |                          | Cycle 7 and Cycle 11 only
(predose) j |
| Serum for ADA                          |                   | X (predose) k                           | X (predose) k |                          |                          | Cycle 7 and Cycle 11 only
(predose) k |
| Study drug administration l |                   | According to each study drug-specific regimen      |                          |                          |                          |   |

ADA = antidrug antibody; AE = adverse event;  $\beta$ -hCG = beta human chorionic gonadotropin; CT = computed tomography; CCI [REDACTED]

ECG = electrocardiogram; ECOG = Eastern Cooperative Oncology Group; EOI = end of infusion; HBc = hepatitis B core; HBs = hepatitis B surface; HBsAg = hepatitis B surface antigen; HBV = hepatitis B virus; HCV = hepatitis C virus; HIV = human immunodeficiency virus; MRI = magnetic resonance imaging; PET = positron emission tomography; PK = pharmacokinetics; SAE = serious adverse event; T3 = triiodothyronine; T4 = thyroxine; TSH = thyroid stimulating hormone.

Note: All safety laboratory results must be reviewed by the investigator or physician designee prior to administration of any study treatment.

a Diagnosis of active tuberculosis is defined by compatible clinical evaluation (medical history and physical examination), radiographic findings, and tuberculosis testing in line with local practice.

b In cases when the first ECG shows clinically significant abnormalities, including a QTcF value  $\geq$  470 ms, 2 additional ECGs should be obtained over a brief period (eg, 30 minutes) to confirm the finding based on the average of all 3 manually overread ECGs by a medically qualified delegate.

